Primary Efficacy Objective: Evaluate the efficacy of treatment at Day 28 following high-titer Anti- SARS-CoV-2 plasma versus control (SARS-CoV-2 non-immune plasma) in subjects exposed to COVID-19 at day 28.

Primary Endpoint: Cumulative incidence of development of COVID-19 disease (symptoms compatible with infection and/or + molecular testing) regardless of disease severity.

Primary Safety Objective: Evaluate the safety of treatment with high-titer Anti- SARS-CoV-2 plasma versus control (SARS-CoV-2 non-immune plasma) in subjects exposed to COVID-19

Primary Safety Endpoints:

1. Cumulative incidence of serious adverse events categorized separately as either severe infusion reactions and ARDS during the study period
2. Cumulative incidence of grade 3 and 4 adverse events during the study period

Secondary Objectives:

1. Cumulative incidence of disease severity between the anti-SARS-CoV-2 convalescent plasma and control groups after individuals develop SARS-CoV-2 infection. Severity of disease will be measured using a clinical event scale of disease severity (evaluated up to Day 28):
 1. Death
 2. Requiring mechanical ventilation and/or in ICU
 3. non-ICU hospitalization, requiring supplemental oxygen;
 4. non-ICU hospitalization, not requiring supplemental oxygen;
 5. a stay of >24 hours for observation in an ED, field hospital, or other healthcare unit*
 6. any receipt of O2 for >24 hours, outside of hospital*
 7. Not hospitalized, but with clinical and laboratory evidence² of COVID-19 infection

² Positive molecular testing for SARS-CoV-2

*with surge of infections in December 2020 and hospitals becoming more full, these two were put into the clinical events scale as hospitalization equivalents

Other Objectives:

1. Compare the anti-SARS-CoV-2 convalescent plasma and control (SARS-CoV-2 non-immune plasma) groups' anti-SARS-CoV-2 titers at days -1 to 0, 1, 7, 14 and 90.
2. Compare the rates and duration of SARS-CoV-2 molecular testing positivity amongst the anti-SARS-CoV-2 convalescent plasma and control (SARS-CoV-2 non-immune plasma) groups at days 1, 7, 14 and 28
3. Compare the levels of SARS-CoV-2 RNA amongst the anti-SARS-CoV-2 convalescent plasma and control (SARS-CoV-2 non-immune plasma) groups at days -1 to 0, 1, 7, 14 and 28

Table of Contents

1. PROTOCOL SUMMARY:	1
1.1. STUDY POPULATION:	5
1.1.1. Inclusion Criteria for Enrollment:	5
1.1.2. Exclusion Criteria	5
2. LIST OF ABBREVIATIONS:	5
3. BACKGROUND AND SCIENTIFIC RATIONALE	6

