Our analysis will be a time to event analysis examining the effect of anti-SARS-CoV-2 plasma. We will estimate the survival function for each treatment arm in order to estimate the risk difference over time as well as the restricted mean survival time which is the area under the survival function and provides the expected mean time to hospitalization or death up to time t^{22} . Our approach will be to estimate the cumulative incidence using the doubly robust estimator based upon targeted minimum loss based estimator as described by Diaz et al [Díaz, I., Colantuoni, E., Hanley, D.F. *et al.* Improved precision in the analysis of randomized trials with survival outcomes, without assuming proportional hazards. *Lifetime Data Anal* **25**, 439–468 (2019)]. By adjusting for baseline covariates that are related to the outcome, we increase precision. The TMLE based approach was shown to increase precision by around 10% to 20% over an inverse probability weighted or augmented inverse probability weighted estimator. As stated above, we will use a hybrid approach of adjusting for pre-specified variables (age) and an algorithmic approach to identify additional variables related to the outcome. Specifically, a random survival forest will be used to identify variables that are related to the outcome in order to increase precision. We will use a random survival forest blinded to the treatment arm allocation and *not* including an indicator variable for treatment. The following pre-randomization variables will be considered: clinical site, race, ethnicity, sex, category of exposure, hematology factors and other laboratory markers (i.e., CBC and metabolic panels), body mass index, ABO blood group, targeted physical exam, and prior comorbidities that have specifically been associated with worse COVID-19 outcomes including: asthma, chronic kidney disease, chronic lung disease (COPD, idiopathic pulmonary fibrosis, cystic fibrosis), diabetes, hemoglobin disorders (thalassemia, sickle cell disease), immunocompromised (cancer, HIV, organ transplantation, prolonged use of corticosteroids), chronic liver disease,

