5.2.2. Analysis of disease severity

A secondary hypothesis is that individuals receiving anti-SARS-CoV-2 convalescent plasma are likely to have less disease severity than control. Therefore, this analysis is restricted to individuals who have developed a SARS-CoV-2 infection. We have devised a clinical event scale for disease severity based on the COVID clinical severity scale which is composed of clinical events that range from being symptomatic and not hospitalized, to being hospitalized, to mechanical ventilation/ICU, to death.

We will separately analyze each of the clinical events by determining the cumulative incidence from time from randomization. Similarly to the primary analysis, we will utilize the TMLE based estimator and adjust for age and any pre-specified candidate variables selected via the algorithm as described above. If individuals jump in severity (e.g., progress from symptomatic not hospitalized to ICU without being hospitalized in non-ICU) then we will interval censor the lower events between the two time points prior to more severe and time of severe clinical event. This will allow individuals to contribute to the progression through the clinical events.

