## Secondary Analyses:

A secondary hypothesis is that individuals receiving anti-SARS-CoV-2 convalescent plasma are likely to have less disease severity than control. We have devised a clinical event scale for disease severity based on the COVID clinical severity scale which is composed of clinical events that range from being not infected to death. The event scale is as follows:

1. Death
2. Requiring mechanical ventilation and/or in ICU
3. non-ICU hospitalization, requiring supplemental oxygen;
4. non-ICU hospitalization, not requiring supplemental oxygen  
or  
a stay of >24 hours for observation in an ED, field hospital, or other healthcare unit\*  
or  
any receipt of O2 for >24 hours, outside of hospital\*
5. Not hospitalized, but with clinical and laboratory evidence of COVID-19 infection (symptomatic infection)

---

 Positive molecular testing for SARS-CoV-2

\*with surge of infections in December 2020 and hospitals becoming more full, these two were put into the clinical events scale as hospitalization equivalents

6. Not hospitalized, no clinical symptoms compatible with COVID-19, but with laboratory evidence of COVID-19 infection (asymptomatic infection)
7. No symptoms compatible with infection, no laboratory evidence of COVID-19 (No indication of infection)

This analysis will be done using the status of participants by day 32 (corresponding to day 28 visit allowing for window around the scheduled visit) using a doubly robust estimators for ordinal outcomes and adjusted for the pre-specified candidate variables selected via the algorithm as described above. The doubly robust estimator that will be used is that as outlined by Benkeser et al. (2020) based upon a non-parametric extension of the log-odds ratio by Diaz et al. (2016). A sensitivity analysis will be done in which participants who have indication of positive infection (e.g. clinical scale event <7) at  $\leq 3$  days after transfusion.

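### Protocol 5.2.2 interval-censors severity levels that a participant is known to have skipped, so its level-by-level incidences count events that did not occur or, read as 'this level or worse', blur a known date

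*Protocol*

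**What the plan says.** Protocol 5.2.2 limits the severity analysis to participants who have become infected and then sets the estimand: "We will separately analyze each of the clinical events by determining the cumulative incidence from time from randomization". For estimation, "we will utilize the TMLE based estimator and adjust for age and any pre-specified candidate variables selected via the algorithm". That points back to the primary analysis in Protocol 5.2: "Our approach will be to estimate the cumulative incidence using the doubly robust estimator based upon targeted minimum loss based estimator".

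For a participant who jumps in severity, "then we will interval censor the lower events between the two time points prior to more severe and time of severe clinical event". The example is people who "progress from symptomatic not hospitalized to ICU without being hospitalized in non-ICU". The stated purpose is: "This will allow individuals to contribute to the progression through the clinical events".

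The SAP (Secondary Analyses) handles the same hypothesis differently. It compares status by day 32 on a seven-level scale that includes uninfected participants, "using a doubly robust estimators for ordinal outcomes". It has no jump rule and no restriction to the infected. The SAP's Study Design section still frames the secondary outcome as a cumulative incidence of severity.

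The scales also differ:
- The Protocol summary has seven levels. Observation stays and oxygen outside hospital are separate levels, with the footnote "with surge of infections in December 2020 and hospitals becoming more full, these two were put into the clinical events scale as hospitalization equivalents".
- Protocol 4.1.3 and 6.1 have five levels, without those two.
- The description in 5.2.2 also omits them.
- The SAP groups both with non-ICU hospitalization without oxygen.

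**The concern.** Interval censoring describes an event that happened on an unknown date within a known interval. In the example in 5.2.2 the non-ICU stay did not happen. Entering it as interval-censored turns a known absence into an event with an uncertain date. Because each event is analysed separately and nothing in 5.2.2 says 'or worse', the result for that level is no longer the incidence of that level.

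The analysis set is small, so a few such participants can move a level's estimate visibly. A reader of the per-level results could conclude that participants had milder hospital stays that they never had.

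**Working it through.** **1. The plan's own figure.** It matters here only because it fixes the expected number of infected participants. Inputs from Protocol 5.1 and SAP Power and Sample Size: 13% control, 6.5% HCIP, one-sided alpha 0.05, power 0.80, 1:1 allocation, stated total 488.
- Exponential hazard ratio: ln(1 − 0.065) / ln(1 − 0.13) = 0.4826.
- Events (Schoenfeld): 4 × (1.645 + 0.842)² / (ln 0.4826)² = 46.6.
- Mean event probability: (0.13 + 0.065) / 2 = 0.0975.
- Total: 46.6 / 0.0975 = 478, which is 2.1% below 488. All eight cells of SAP Table 1 reproduce within 3% in the same way.

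**2. Size of the analysis set.** With 250 per arm:
- Control: 250 × 0.13 = 32.5.
- HCIP: 250 × 0.065 = 16.25.
- Total: 48.75.

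**3. What the rule does to a skipped level.** An observation censored to the interval (L, R] contributes F(R) − F(L) to the likelihood, where F is the cumulative incidence. If R, the date of the severe event, is no later than day 28, all of its mass falls by day 28. It is an event with probability 1, and only its date is uncertain.

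**4. Effect per jumper on the skipped level's day-28 incidence.**
- Control: 100 / 32.5 = 3.1 percentage points.
- HCIP: 100 / 16.25 = 6.2 percentage points.

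**5. Illustration.** The documents give no severity distribution, so these counts are assumed. The rule's value is the non-parametric (Turnbull) estimate at day 28.

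| Infected | Actual non-ICU stays | Direct-to-ICU jumpers | True incidence of the level | Under the rule | Non-ICU stay or worse |
|---|---|---|---|---|---|
| 32 (control) | 4 | 1 | 12.5% | 15.6% | 15.6% |
| 32 (control) | 4 | 2 | 12.5% | 18.8% | 18.8% |
| 32 (control) | 4 | 3 | 12.5% | 21.9% | 21.9% |
| 16 (HCIP) | 2 | 1 | 12.5% | 18.8% | 18.8% |
| 16 (HCIP) | 2 | 2 | 12.5% | 25.0% | 25.0% |

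The last two columns agree in every row. The rule returns the incidence of 'this level or worse', while 5.2.2 describes a separate analysis of each event.

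**6. Timing under the 'or worse' reading.** A participant who goes straight to ICU first reaches 'non-ICU hospitalization or worse' on the ICU date. That date is known. The rule replaces it with an interval ending there, so the curve can only move earlier. The limits of that interval are also not clear from the wording.

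**7. Estimator.** Set 5.2.2 beside Protocol 5.2.4. For duration of molecular-test positivity, 5.2.4 uses interval censoring correctly: the changes of status occurred, between known visits. It names non-parametric or, more likely, parametric models for those data. Section 5.2.2 names the TMLE, and neither document says how interval-censored times enter it.

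**The case against.** The strongest reply is that the sentence about progression shows a cumulative intent, with each level meaning that severity or worse. On that reading the day-28 value is correct, as step 5 shows. This stands as far as it goes. But 5.2.2 never defines the events that way, and the rule then blurs a date that is known.

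A second reply is that the SAP is later and does not use the rule. The Protocol is dated December 23, 2020, and the SAP cites a list as updated on 5/29/2021. This also stands and limits the reach of the fault. It does not remove it: 5.2.2 is current text, and it is the only place that says how to compute a level-by-level incidence.

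Third, severity is assessed at scheduled contacts, so a participant may pass through a level between contacts at an unrecorded time. Interval censoring is proper there. The rule fails because it does not separate that case from a true skip.

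Three stronger inferences are tempting, and the documents do not support them:
- *Every direct admission is also counted as an observation stay and as home oxygen.* These are separate levels only in the Protocol summary. They are absent from 4.1.3, 6.1 and the description in 5.2.2, and the SAP merges them into one level. The summary itself calls them equivalents of hospitalization, so a direct admission need not be a jump over them.
- *The analysis cannot be run.* That would rest on the cited TMLE paper. The documents show only that the handling is not specified.
- *A trial-wide count of false events, or a bias that differs by arm.* Either would need admission rates, oxygen shares or patterns of worsening that the documents do not give.

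**Conclusion.** The concern holds for the Protocol's level-by-level severity analysis and no further. Read literally, 5.2.2 counts a level known to have been skipped as having occurred by day 28, adding about 3 percentage points per jumper in control and 6 in HCIP. Read as 'this level or worse', the day-28 value is right; what remains is a missing definition and a known date moved into an earlier interval.

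The size assumes 250 per arm and takes the planning rates for symptomatic disease as the number infected. If asymptomatic infections are also in the analysis set, the denominators grow and the effect per jumper shrinks. The number of jumpers is unknown.

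A reader might infer that the trial's severity result is compromised. It is not if the SAP is followed, because its ordinal analysis does not use the rule. The two plans do conflict in population, estimand and estimator, and that should be settled before analysis. This should be corrected, but it does not touch the primary analysis.

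**What to change.** 1. Name the SAP ordinal analysis as the single tested severity analysis. Align Protocol 5.2.2 with it in population, time point and scale, with the two hospitalization equivalents grouped as in the SAP.
2. If level-by-level cumulative incidence is kept, label it supportive. Define each event as 'level k or worse', dated at the first observed occurrence of that level or any worse one, and right-censored at last contact or the end of the window.
3. Limit interval censoring to levels actually passed through at an unrecorded time, and say how those times enter the estimator. Do not apply it to levels known to have been skipped.
4. Tabulate the worst level actually observed for each participant, by arm.

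The cost is wording in the Protocol and SAP, and the analysis becomes simpler. The small downside is that nested thresholds are correlated with each other and do not describe single levels; the table in item 4 supplies that description.

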5.2.3. Analysis of anti-SARS-CoV-2 titers

Analysis of titers will also primarily be descriptive, comparing the geometric mean titers at days 0, 1, 7, 14, and 90 between the randomized arms. Furthermore, it is of interest to describe the entire distributions of anti-SARS-CoV-2 titers by randomized arms and contrast these distributions. Therefore, we will use quantile regression in order to describe whether

there is a shift or change in the titer distribution between randomized arms [Roger Koenker, Quantile Regression. Cambridge University Press, May 5, 2005]. Quantile regression does not require the assumption of a parametric or any other type of distribution as it identifies the titer at each percentile (e.g., what is the 10th, the 15th, ..., 50th [the median], ..., 90th percentiles of anti-SARS-CoV-2 titers). Given that this is a repeated measurement at days 0, 1, 7, 14, and 90 we will account for the correlation within individuals using a cluster bootstrap in order to properly estimate the p-value and 95% confidence intervals.

5.2.4. Analysis of rates and duration of SARS-CoV-2 molecular testing positivity

Analysis of the rate and duration of SARS-CoV-2 molecular testing positivity between the randomized arms will primarily be descriptive examining proportion positive at days 0, 1, 7, 14, and 28 and then among those who are positive whether individuals lose positivity status at a subsequent visit. To determine the proportion that are positive at each visit, we will do a pooled complementary log-log model in order to describe the cumulative incidence of SARS-CoV-2 molecular testing positivity over time. The pooled complementary log-log model is a discrete time-to-event-analysis that estimates the log hazard rate at each discrete time point. From this a cumulative incidence of positivity can be estimated. To determine the duration of positivity, the analysis is complicated by the exact day that an individual becomes positive and the exact day that an individual becomes negative is not known since SARS-CoV-2 molecular testing positivity will only be acquired at days 0, 1, 7, 14, and 28. However, we can estimate a minimum and maximum amount of time that an individual was positive. For instance if an individual first positive visit is at day 1 and then is positive at day 7 but negative at day 14, then we know that this individual became positive between day 0 and 1 and negative between day 7 and 14. Therefore, the minimum amount of time positive is 7 days (day 8 – day 1) and the maximum is 14 days (day 14 – day 0). Therefore, we can interval censor these individuals. That is we know that the duration is between 7 and 14 days for this example individual. Across all individuals we can describe the duration of positivity either using a non-parametric approach for time-to-event analysis, but more likely given the sample size a parametric model. We will assess several parametric distributions aiming for parsimony in the number of parameters being estimated due to the interval censored data which results in increased uncertainty in the model. To determine the best model, we will use Akaike's Information Criterion (AIC) to choose the best model fit. However, if the sample that becomes positive is really small, then we will only be able to describe the observations without a formal statistical model.

5.2.5. Analysis of SARS-CoV-2 RNA

Similar to the secondary aim of comparing the anti-SARS-CoV-2 titers, the goal of this secondary aim is to describe the distribution of SARS-CoV-2 RNA between randomized arms. Therefore, we will use the same approach as above of applying quantile regression.

5.3. Endpoints

Primary Efficacy Endpoint:

28 day incidence of COVID-19 infection with both clinical and laboratory evidence.

Primary Safety Endpoints:

1. Cumulative incidence of serious adverse events categorized separately as either severe infusion reactions and ARDS during the study period
2. Cumulative incidence of grade 3 and 4 adverse events during the study period

Secondary Endpoints

1. 28 day incidence of severe COVID-19 infection defined by death or initiation of mechanical ventilation.
2. Anti-SARS-CoV-2 titers at days -1 to 0, 1, 7, 14, and 90.
3. Rates and duration of SARS-CoV-2 molecular testing positivity at days 1, 7, 14, and 28.

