5.2.1. Analysis of AE data

Analysis of AE data will primarily be descriptive based on MedDRA coding of events. The proportion of subjects experiencing an SAE and the proportion experiencing a Grade 3 or higher. AE will be compared between randomized arms using Fisher’s Exact Test.

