7. RISKS AND BENEFITS

Potential Benefits of treatment

The potential benefits of antiviral treatment with anti-SARS CoV-2 plasma in patients at high risk for developing COVID-19 due to a close contact with another individual with COVID-19 are unknown. However, it is anticipated that treatment will decrease the risk of developing symptomatic disease and decrease the severity of illness should it develop.

Potential benefits of clinical monitoring and virologic testing

Subjects enrolled in the study will undergo close clinical and virologic monitoring that could facilitate earlier diagnosis of development of COVID-19 with associated benefit to the individual, their family and the community at large.

Potential risks

1. Risks of plasma: Fever, chills, rash, headache, serious allergic reactions, TRALI, TACO, transmission of infectious agents
2. Risks of phlebotomy: local discomfort, bruising, hematoma, bleeding, fainting,
3. Total blood draws will not exceed 500 mL
4. Risks of oropharyngeal and throat swab: local discomfort, vomiting

Alternatives

The alternative to participation in this study is routine care and monitoring following close contact with an individual with COVID-19

Safety measures

1. Safety Evaluations will assess for the safety of high titer anti-SARS-CoV-2 plasma and determine if it is higher, lower or the same as SARS-CoV-2 non-immune plasma
2. Clinical evaluations: In-person vital signs and symptom screen on days 0,1,7,14 and remote (phone call) symptom screens on days ,3 and 60
3. Laboratory evaluations

4. Safety laboratory tests (ABO typing, pregnancy testing, CBC and comprehensive metabolic panel) will be performed at the local CLIA-certified clinical laboratory on days -1 to 0, 1, 7 and 14

Event (AE)

Any untoward medical occurrence in a clinical investigation subject who has received a study intervention and that does not necessarily have to have a causal relationship with the study product. An AE can, therefore, be any unfavorable and unintended sign (including an abnormal laboratory finding, for example), symptom, or disease temporally associated with the use of the study product, whether or not considered related to the study product.

Serious Adverse Event (SAE)

An SAE is any adverse event that results in any of the following outcomes:

1. Death;
2. Life-threatening (immediate risk of death);
3. Inpatient hospitalization or prolongation of existing hospitalization;
4. Persistent or significant disability or incapacity;

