## **Adverse events of study treatment:**

We hypothesize that participants randomized to convalescent plasma will not have any increased risk to standard transfusions. Preliminary data from the expanded access protocol for treatment of COVID-19 by convalescent plasma among those with severe disease, suggests that the treatment is safe with low number of adverse events [Joyner et al, J Clin Invest. 2020].

Adverse event data will be collected continuously throughout the trial and analyzed by treatment group at each interim analysis. We will also compare the rates of all serious adverse events (as

specified by the Health and Human Services definition) using cumulative incidence. The primary safety endpoints are i) the cumulative incidence of treatment-related serious adverse events categorized separately as either severe infusion reactions or Acute Respiratory Distress Syndrome (ARDS) during the study period and ii) cumulative incidence of treatment-related grade 3 and 4 adverse events during the study period.

Data collection for adverse events will be done via a combination of specific questions for anticipated effects and spontaneous participant report. We will present overall number of AEs and SAEs by treatment group and where differences exist, we will present those by organ system. As these are descriptive safety analyses no correction for multiplicity will be undertaken.

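### The second primary safety endpoint stops at grade 4, although death is grade 5 and the protocol's own analysis uses grade 3 or higher; the SAP narrows it further to treatment-related events

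*Protocol*

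**What the plan says.** - **Endpoint, protocol.** The protocol summary (Section 1) and Section 5.3 both give the second primary safety endpoint as "Cumulative incidence of grade 3 and 4 adverse events during the study period".
- **Endpoint, SAP.** The section on adverse events of study treatment gives "cumulative incidence of treatment-related grade 3 and 4 adverse events during the study period". The treatment-related limit is not in the protocol.
- **Severity scale.** Protocol Section 7.1 has five grades. Life-threatening events are grade 4, and death has its own grade, 5.
- **Analysis, protocol.** Section 5.2.1 names two quantities: "The proportion of subjects experiencing an SAE and the proportion experiencing a Grade 3 or higher". A stray full stop splits the sentence; the words that follow, "AE will be compared between randomized arms using Fisher", identify Fisher's exact test.
- **Analysis, SAP.** All SAEs are to be compared by cumulative incidence, and AE and SAE counts shown by arm. There is no comparison of grade 3 or higher.
- **First primary safety endpoint.** In Section 5.3 it is "Cumulative incidence of serious adverse events categorized separately as either severe infusion reactions and ARDS during the study period". The SAP version is also limited to treatment-related events.
- **SAE definition.** Protocol Section 7 begins "An SAE is any adverse event that results in any of the following outcomes", and death is the first outcome listed.

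**The concern.** A severity endpoint is normally open at the top, so that a worse outcome cannot fall outside it. Here the cut at grade 4 leaves out the one grade reserved for death, and the companion endpoint takes a death only if the event was ARDS or a severe infusion reaction. Protocol Section 3.2 mentions late acute renal failure and thromboembolic events as rare complications of plasma. A fatal event of that kind, recorded only as grade 5, would be in neither primary safety endpoint.

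The two documents would also give different primary safety results from the same data. An analyst following Section 5.2.1 counts grade 5 whatever its cause. One following the SAP leaves it out, and leaves out every unrelated grade 3 or 4 event as well. Section 7.1 has the investigator classify an event as not associated if another etiology appears to explain it. A serious course of COVID-19 has an obvious other explanation, yet antibody-dependent enhancement is the harm that Section 8.3 singles out.

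**Working it through.** **1. Which events each text counts**

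| Place | Grades counted | Limited to treatment-related? | Grade 5 included? |
|---|---|---|---|
| Protocol summary; Section 5.3 | 3, 4 | No | No, read literally |
| Protocol Section 5.2.1 | 3 and above | No | Yes |
| SAP, adverse events section | 3, 4 | Yes | No, read literally |

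These are three different sets of participants under what should be one endpoint.

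**2. The plan's own figures on deaths**

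Protocol Section 8.3, Table 1, gives the probability of at least one death, 1 − (1 − f)^n, with n expected symptomatic participants and case fatality f.

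- Control, n = 15: 0.1906 at f = 1.4% and 0.3367 at 2.7%. The table has 0.191 and 0.337.
- HCIP, n = 4: 0.0548 and 0.1037. The table has 0.055 and 0.10.

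The table reproduces. It rests on 75 per arm with 20% and 5% symptomatic, not on the final sample size.

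**3. Expected COVID-19 deaths at full size**

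Inputs: 500 randomized 1:1, so 250 per arm; symptomatic incidence 13% control and 6.5% HCIP (Protocol Section 5.1); case fatality 1.4% to 2.7% (Section 8.3).

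- Control: 250 × 0.13 × 0.014 = 0.455; 250 × 0.13 × 0.027 = 0.878.
- HCIP: 250 × 0.065 × 0.014 = 0.228; 250 × 0.065 × 0.027 = 0.439.

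The binomial probability of two or more HCIP deaths (n = 250, probability 0.065 × f) is 2.2% at f = 1.4% and 7.2% at f = 2.7%. These figures cover COVID-19 deaths only; the documents give no rate for other deaths. They are also upper limits on what the endpoint would lose under these assumptions, because a death that also has a grade 3 or 4 record still counts.

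**4. What the wording could do if there were excess deaths**

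The counts here are assumed, not taken from the plan: 250 per arm, 12 participants per arm whose worst event is grade 3 or higher, no control deaths, and every HCIP death recorded only as grade 5.

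| HCIP deaths | Grade 3–4 only, HCIP v control | Fisher p (two-sided) | Grade 3 or higher |
|---|---|---|---|
| 2 | 10 v 12 (4.0% v 4.8%) | 0.83 | 12 v 12 (4.8% v 4.8%) |
| 4 | 8 v 12 (3.2% v 4.8%) | 0.49 | 12 v 12 |
| 6 | 6 v 12 (2.4% v 4.8%) | 0.23 | 12 v 12 |

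The point estimate moves in favour of the arm with the deaths, though even six such deaths do not produce a significant difference. The result depends entirely on the assumption that no fatal case has a separate grade 3 or 4 record.

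**The case against.** The strongest reply is that deaths are well covered elsewhere:

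- Section 5.2.1, the protocol's only stated test of graded events, includes grade 5 and also compares all SAEs.
- The SAP compares all SAEs and, under Statistical Principles, treats a death without known infection as an infection.
- Death is the top level of the severity scale in both documents.
- Protocol Section 8.3 has deaths counted by arm and each assessed for relation to plasma, and the SAP's stopping guidelines give deaths in the HCIP arm special attention.

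All of this stands. A reader might infer that such a death disappears from the safety assessment, or surfaces only in a general SAE table. The documents do not support that.

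A reader might also infer that a participant who worsens from grade 4 to death leaves the numerator. That holds only if each event keeps just its final grade, and neither document says so. Under a cumulative incidence, a grade 4 event already recorded continues to count. Equally, neither document states a worst-grade rule, so the question is open rather than settled in the plan's favour.

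Finally, ARDS, which Section 8.3 names as a possible sign of enhancement, is in the first primary safety endpoint, so some enhancement-related deaths would be caught there. The documents give no figure for that share, and the SAP's treatment-related limit applies to that endpoint too.

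What the reply does not remove is the mismatch itself. The SAP contains no grade 3 or higher comparison, so Section 5.2.1 does not repair the SAP's endpoint. The severity scale is evaluated to day 28 (day 32 in the SAP's analysis), while Protocol Section 6 schedules AE evaluation at day 60, so the scale cannot stand in for the safety endpoint on later deaths.

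**Conclusion.** The concern holds as an inconsistency in a stated primary safety endpoint. The summary, Section 5.3 and the SAP stop at grade 4; Section 5.2.1 does not; and the SAP alone limits the endpoint to treatment-related events. Read literally, a death with no separate grade 3 or 4 record that is neither ARDS nor a severe infusion reaction is in neither primary safety endpoint.

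On the plan's assumptions the numerical effect is small: fewer than one COVID-19 death expected per arm, and a 2.2% to 7.2% chance of two or more in the HCIP arm. It would matter mainly if HCIP caused excess deaths, which is the case a safety endpoint is there to detect.

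It would go too far to conclude that the arm with more deaths will look safer. That needs excess deaths, no grade 3 or 4 record for them, and a reader who looks at this one endpoint alone. The plan should be corrected before analysis, but its overall safety monitoring is not undermined.

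**What to change.** 1. In the protocol summary, Protocol Section 5.3 and the SAP's adverse events section, define the endpoint as the cumulative incidence of grade 3 or higher adverse events (grades 3 to 5), counting each participant once at the worst grade. This matches Section 5.2.1 and settles the counting rule.
2. In the SAP, remove the treatment-related limit from this endpoint, or report treatment-related events only as an additional breakdown. Changing the grades alone would still exclude every death judged unrelated, so the SAP would still not match Section 5.2.1. Reconcile the same limit in the SAP's version of the first primary safety endpoint.

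The cost is a wording change in three places. Severity and association are already assessed for each event under Protocol Section 7.1, so no new data are needed, and the sample size and efficacy analysis are unaffected.
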